Statistical Analysis Plan (SAP)

This plan, or SAP Addendum, provides additional detail to the statistical considerations that were documented in the statistical analysis plan in Health4Her-Automated Protocol_V4_11 08 2023 (available via the [trial record](#) on ClinicalTrials.gov).

Additional analyses not specified in the published protocol or this addendum will be regarded as exploratory.

Statistical software

Analyses will be conducted using the most appropriate procedures in programs such as GenStat, R, SAS, or Stata.

Analytic approach

Data will be collated, cleaned, and validated using programmed edit checks.

The analysis will take place based on the intention to treat (ITT) principle (i.e. subjects' data are analysed as randomised) after all subjects, not known to have withdrawn or not deemed lost to follow-up, have had their 4-week assessments.

Outcome variables with repeated measurements will be analysed by fitting Generalised Linear Mixed Models (GLMMs) with an appropriate link function (e.g. gaussian for continuous outcomes or outcomes treated as continuous [e.g. 5-point Likert scales] and logit for binary outcomes). Inferences about the effect of the Health4Her intervention on the outcomes will be based on a comparison, between treatment groups, of change in outcomes from baseline to immediate post-intervention (i.e. immediately post-randomisation) and/or 4-weeks post-randomisation. Models will estimate fixed effects for treatment and time, and their interaction, and random effects for subjects and assessments within subjects. If necessary, suitable variance-covariance structures for the repeated measures will be compared using Akaike's Information Criterion and/or Bayesian Information Criterion. In the case that GLMMs have estimation/convergence difficulties regression models may be estimated via Generalised Estimating Equations (with an appropriate link function). A Wald test (or equivalent approach) will be used to test for an overall group by time interaction in outcomes.

Outcome variables without a baseline assessment will be examined using Generalised Linear Models (i.e. the non-mixed model version). Inferences about the effect of the Health4Her intervention on these outcomes will be based on a comparison between treatment groups of outcomes assessed at 4-weeks post-randomisation. Models will estimate fixed effects for treatment.

All statistical tests will be two-tailed with the alpha level set to 0.05.

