Randomisation, interventions and procedure: The study will be described as the “Health4Her women’s health study” to minimise the salience of the trial’s alcohol focus, and to increase its relevance for all women. In the active and control arms, participants will be provided with an iPad and earbuds, and will self-complete consent (via a landing page) and baseline assessment before being randomly assigned (1:1 allocation ratio, utilising a “permuted blocks of variable size” scheme embedded in the iPad) to receive 1) ~4 minutes of alcohol brief intervention plus ~3 minutes of lifestyle information (active arm: H4H-A), or 2) ~3 minutes of lifestyle information not inclusive of alcohol information (control arm) via interactive animation. An assessment immediately post-intervention will be completed on the iPad (comprising only the set of intention questions containing the primary outcome item). A 4-week follow-up assessment will be completed offsite via online survey, with the follow-up researcher prompting/assisting with survey completion when required.

Alcohol brief intervention (active arm): Finalised through the collaborative design process, and based on brief intervention and applied behaviour change principles, the alcohol brief intervention will include information and behaviour-change content regarding alcohol consumption such as: messaging around alcohol risks/harms, positive-framed messaging on the health benefits of reducing alcohol intake, and behaviour change strategies (e.g. drink counting, goal setting, behaviour substitution, problem solving) (12, 23-26). This iteration of the research provides an opportunity to refine and add to the evidence-based intervention elements utilised in the pilot (e.g. provide the intervention in ‘chunks’, where the participant will view 1-2 minutes of animation before completing a brief activity such as setting goals or problem solving strategies), with the goal of strengthening intervention response. **NB.** H4H-A will be aligned with the National Health and Medical Research Council’s recently revised Australian Alcohol Guidelines (i.e. no more than 10 standard drinks per week, with the message ‘the less you drink, the lower your risk of alcohol-related harm’). Post-session information will be provided via email (i.e. an electronic brochure summarising alcohol brief intervention content).

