While this study will examine reach, uptake, feasibility and acceptability as important end-points, it will be powered to test the effectiveness of H4H-A in decreasing women's drinking intentions. The sample size has been calculated using data from a previous, related study examining the effects of alcohol warning information about the alcohol-breast cancer link on drinking intentions (15). Using a Likert 5-point response scale (1 = not at all, 5 = to a very great extent, this study showed that the warning information, *Alcohol increases your risk of breast cancer*, increased participants' intention to reduce the amount of alcohol they consume from a pre-exposure mean of 2.37 (SD = 1.18) to a post-exposure mean of 2.63 (SD = 1.22).

Given some differences in the previous study (i.e. the message about alcohol and breast cancer risk was not personally relevant to the whole sample comprising males and females 18-65 years; a single health message was provided, which is different to the Health4Her intervention containing several 'active ingredients' based on alcohol brief intervention and applied behaviour change principles), we anticipate a greater increase in participants' intention to reduce the amount of alcohol they consume in the current study. Further, based on our previous research, we anticipate some assessment reactivity among the control group.

Power and sample size estimations were conducted using General Linear Mixed Model Power and Sample Size (GLIMPSE) software. We estimate (factoring in 5% attrition, and 30% of women attending breast screening who do not drink or have not drunk in the past month) that a total sample size of at least 78 (39 per group) will have 80% power ($\alpha < 0.05$) (a total sample size of 90 [45 per group] will provide 85% power, $\alpha < 0.05$) to detect a change in women's drinking intentions of 2.37 to 3.37 (change = 1.00) in the intervention group, and a change of 2.37 to 2.63 (change = 0.26) in the control group between baseline and immediately post-intervention. Therefore, this study will aim to recruit a total

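### The covariance structure for the primary three-visit outcome is left to an unspecified data-driven choice, so the primary standard error can be wrong in either direction and can be settled after the data are seen.

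*SAP*

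**What the plan says.** Under Analytic approach, the SAP treats the Likert item as continuous. It fits a Gaussian mixed model with treatment, time and their interaction, and "random effects for subjects and assessments within subjects". Other structures come in only if judged necessary, in which case "suitable variance-covariance structures for the repeated measures will be compared using Akaike's Information Criterion and/or Bayesian Information Criterion". The SAP lists no candidate structures, says nothing about what triggers the comparison, and gives no rule for conflicting criteria. It does not mention robust standard errors. GEE appears only as a fallback for estimation or convergence difficulties. On testing, "All statistical tests will be two-tailed with the alpha level set to 0.05".

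The schedule in protocol section 6.2 has the primary item at three visits. Section 4.2 places the first two in one session on site: "An assessment immediately post-intervention will be completed on the iPad", after about 3 minutes (control) or 7 minutes (active) of content. The third is an online survey four weeks later. The power statement in section 4.2 gives means, SDs and deductions for attrition and non-drinkers, but no within-subject correlation.

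**The concern.** With one score per assessment, an assessment-level random effect cannot be separated from the residual. The starting model is therefore compound symmetry (CS): one variance and one correlation shared by all three pairs of visits. The schedule gives reason to doubt that, since two scores are minutes apart and the third is four weeks away, by a different route.

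Under CS, the standard error of the baseline-to-immediate contrast borrows from the 4-week pairs. If those correlate less strongly, the primary standard error is too large and power is lost, while the 4-week standard error is too small. If they correlate more strongly on average, the primary standard error is too small. The AIC/BIC step could correct this. As written, though, it lets the analyst choose between criteria that often disagree at this sample size, and so choose between two primary standard errors.

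**Working it through.** **Inputs from the documents.** Alpha is 0.05, two-sided. From protocol section 4.2: SDs 1.18 and 1.22; "2.37 to 3.37 (change = 1.00) in the intervention group" and "a change of 2.37 to 2.63 (change = 0.26) in the control group", so the difference in change is 1.00 − 0.26 = 0.74; deductions of 5% and 30%; "a total sample size of at least 78 (39 per group) will have 80% power" and "a total sample size of 90 [45 per group] will provide 85% power".

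**Assumed.** All correlations: r01 (baseline-immediate), r02 (baseline-4 weeks) and r12 (immediate-4 weeks).

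**1. The plan's own power.** Evaluable numbers are 78 × 0.95 × 0.70 = 51.9, about 26 per arm, and 90 × 0.95 × 0.70 = 59.9, about 30 per arm.

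SD of change = √(1.18² + 1.22² − 2·r01·1.18·1.22)

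Power = Φ(0.74 / (SD·√(2/n)) − 1.96)

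- 80% at 26 per arm needs r01 = 0.686 (0.698 with the t distribution). 85% at 30 per arm needs 0.683 (0.693).
- One value, r01 = 0.69, gives an SD of change of 0.946 and powers of 80.6% and 85.8%, so it fits both stated figures.
- Without the deductions (39 and 45 per arm), r01 of about 0.53 also fits both. The correlation behind the plan is therefore not identified.

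**2. If CS is always kept.** With complete data the estimated contrast is the same under either structure, and only its standard error changes. Treating the visit variances as equal:

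k = model SE / true SE = √((1 − mean r)/(1 − r01))

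Power = Φ(2.80 − 1.96k)

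For r01 = 0.70 and r02 = r12 = 0.50, mean r = 0.567, k = √(0.433/0.300) = 1.20, and power = Φ(0.45) = 67%.

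| r02 = r12 (r01 = 0.70) | k | Power under CS |
|---|---|---|
| 0.75 | 0.94 | 83% |
| 0.70 | 1.00 | 80% |
| 0.65 | 1.05 | 77% |
| 0.60 | 1.11 | 74% |
| 0.50 | 1.20 | 67% |
| 0.40 | 1.29 | 61% |

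**3. After the planned selection.** Simulation at 26 per arm, complete normal data, CS (2 parameters) against unstructured (6 parameters), 4,000 trials per row. The Monte Carlo error is about √(0.8 × 0.2/4000) = 0.6 points.

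| r02 = r12 | AIC keeps CS | BIC keeps CS | Power: unstructured | CS always | AIC chooses | BIC chooses |
|---|---|---|---|---|---|---|
| 0.60 | 76% | 98% | 81% | 75% | 78% | 76% |
| 0.50 | 46% | 88% | 81% | 69% | 77% | 71% |
| 0.40 | 23% | 68% | 81% | 62% | 79% | 70% |

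Separate runs of 20,000 trials agreed within about two points. In them, with 4-week correlations of 0.50, the two criteria chose different structures in 43% of trials. In about 6% of trials that disagreement decided whether the primary result was significant.

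**4. The 4-week contrast under CS.** SE ratio = √((1 − mean r)/(1 − r02)) = 0.96, 0.93 and 0.91 for the three rows above. Type I error = 2(1 − Φ(1.96 × ratio)) = 6.1%, 6.8% and 7.4%; simulated 6.1%, 6.6% and 7.2%.

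**5. Other patterns, 39 per arm.**

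- r01 = 0.53 with 4-week correlations 0.50, 0.45 or 0.40: CS power is 78.8%, 76.0% or 74.0% in simulation, against about 79-80% unstructured.
- r01 = 0.5, r02 = 0.5, r12 = 0.7: k = √(0.433/0.5) = 0.93. The primary standard error is now too small. Simulated primary type I error is about 6.7%, and power is 80.9% under CS against 76.6% unstructured.

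**The case against.** A reader might infer that the SAP fixes compound symmetry, and that the primary standard error is therefore about 20% too large and power falls from 80% to about 68%. The documents do not support that, for four reasons.

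- The SAP names a starting model and expressly allows others. A figure near 68% is the power if CS is kept in every trial. In the same scenario the planned selection gives about 77% under AIC and 71% under BIC.
- The 20% needs correlations of about 0.70 and 0.50. Neither document states any correlation, and values that fit the stated power equally well give a loss of only a few points.
- The direction is not known. Minutes apart suggests a high baseline-immediate correlation, but the intervention lies between those scores, and varied response to it would lower that correlation. The two post-intervention scores could be the most alike.
- The inputs to the power software are not shown. If they already described an equal-correlation model, a fall from 80% does not follow.

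All four stand. It is also fair that, where CS overstates the primary standard error, the primary test is conservative (type I error about 1.8% with 4-week correlations of 0.50). A positive primary result would then not be undermined.

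The objection does not supply a rule. The choice of structure remains open, BIC usually keeps CS at this size when the correlations differ as in step 3, and AIC and BIC can lead to different primary conclusions.

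**Conclusion.** The point holds as a pre-specification weakness with a conditional cost. The primary standard error depends on a structure that the SAP does not settle, and it can be wrong in either direction.

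Assuming 26 evaluable per arm and r01 = 0.70, the power lost if CS is always kept runs from nothing (4-week correlations 0.70) to about 19 points (0.40). After the planned selection, with 4-week correlations of 0.60 to 0.40, power is about 76-79% under AIC and 70-76% under BIC. The 4-week intention contrast has a type I error of about 6-7% where CS is kept. With r01 near 0.53 at 39 per arm the primary loss is a few points. If the two post-intervention scores correlate most strongly, the harm is instead a primary type I error of about 6.7%.

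These figures assume complete, normally distributed data. The selection results compare only CS with unstructured, so intermediate candidates would change the retention rates. The weakness is not fatal, but it is worth correcting because the remedy is cheap.

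**What to change.** In the SAP, for the three-visit Likert outcome, pre-specify an unstructured covariance across the three visits with Kenward-Roger degrees of freedom. Fix the fallback order for non-convergence: heterogeneous Toeplitz, then compound symmetry with robust standard errors. Remove AIC/BIC selection for the primary outcome. It would also help to state the within-subject correlation used in the power calculation.

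The cost is a sentence or two of text and four extra covariance parameters (6 against 2), which is small with about 78 women and three visits. Power will be slightly lower than under CS in patterns where CS understates the standard error, but that extra power comes with a type I error above 5%.

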Pilot Arm – active arm but completed post-screening (i.e. offsite on own device)

Inferences about the effect of the Health4Her intervention completed post-screening (i.e. offsite on own device) on outcomes will be based on based on: 1) a comparison of change, in the pilot arm only, from baseline to immediate post-intervention (i.e. immediately post-randomisation) and/or 4-weeks post-randomisation, and 2) a comparison, between treatment groups (i.e. pilot arm vs control; pilot arm vs intervention; acknowledging that assignment to the pilot arm was not randomised), of change from baseline to immediate post-intervention (i.e. immediately post-randomisation) and/or 4-weeks post-randomisation. The analytic methods described above will be implemented here.

Missing data

Where appropriate, missing values will be addressed through maximum likelihood estimation (i.e. in a mixed model) or using multiple imputation.

Sensitivity analyses

Several sensitivity analyses may be performed:

- Using a per-protocol approach, defined as those who received all elements of the intervention.

- Stratified by participants based on those who: a) report drinking any alcohol in the past month, and b) are identified to be drinking at a level exceeding current national guidelines for weekly and/or single day consumption.
- Including relevant covariates (e.g. age, education, CALD, LGBTIQ+A+) as adjustments. Covariates may also be used to stratify analyses.
- Models to examine the robustness of missing data modelling decisions (e.g. including auxiliary variables in models or in complete case data).

Primary Outcome

- 1) Change in next-month drinking intentions (immediate post-intervention)

Secondary Outcomes

- 1) Change in next-month drinking intentions (4-weeks post-randomisation)
- 2) Change in intended number of standard drinks consumed over the next month (4-weeks post-randomisation)
- 3) Proportion of participants intending to reduce their next-month alcohol consumption (immediate post-intervention)
- 4) Proportion of participants intending to reduce their next-month alcohol consumption (4-weeks post-randomisation)
- 5) Proportion of participants accurately identifying alcohol as a clear risk factor for breast cancer (4-weeks post-randomisation)

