We recently completed a world-first trial (N=558), funded by VicHealth and the Eastern Health Foundation, supported by Maroondah BreastScreen (trial site) and BreastScreen Victoria, and approved by the Eastern Health Human Research Ethics Committee (LR19/011/50551), to test the effectiveness of a prototype of an electronic alcohol brief intervention (Health4Her; researcher-

administered screening alcohol questions, intervention activated by the researcher for the participant to view on an iPad alone). The electronic alcohol brief intervention model was chosen to minimise disruption to service workflow and need for human resource to implement within the busy breast screening environment. In this trial, participants reported poor alcohol literacy (4 in 5 did not have knowledge of the alcohol-breast cancer link) and a desire for more information. The Health4Her intervention was found to be highly acceptable to breast screening service consumers. For the primary outcome, there were significant increases in the proportion of participants accurately identifying alcohol as a clear breast cancer risk factor from baseline to 4-weeks in intervention (OR=41.82, 95% CI=17.76, 98.49, $p<0.001$) and control (OR=4.92, 95% CI=2.75, 8.79, $p<0.001$) arms, with a significantly greater increase in the intervention arm ($p_{\text{arm} \times \text{time}} < 0.001$) (Findings are currently under peer-review for publication). BreastScreen staff were highly supportive of the Health4Her intervention as part of routine care, however, the manually delivered intervention, dependent on dedicated human resource to administer, was considered unviable to implement in practice.

As such, the overall aim of this study is to i) collaboratively design an automated alcohol brief intervention with women who participate in breast screening, ii) examine its effects on drinking intentions and alcohol consumption among women attending breast screening service for routine mammography and iii) understand the factors affecting intervention implementation using mixed-methods program evaluation.

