3.1 RANDOMISED CONTROLLED TRIAL OUTCOMES/HYPOTHESES

Primary outcome/hypothesis:

- a) *Change in next-month drinking intentions (primary outcome)*: we hypothesise that there will be a greater change in the extent to which participants intend to reduce the amount of alcohol they consume among intervention participants, relative to control, between baseline and immediately post-intervention (likert scale response item) (15).

Secondary outcomes / hypotheses:

- b) *Change in next-month drinking intentions*: we hypothesise that there will be a greater change in the extent to which participants intend to reduce the amount of alcohol they consume

among intervention participants, relative to control, between baseline and 4-weeks post-intervention (likert scale response item) (15).

- c) *Change in drinking intentions – standard drinks*: we hypothesise that there will be a greater reduction in the intended number of standard drinks consumed over the next month among intervention participants, relative to control, between baseline and 4-weeks (quantity/frequency response items) (16).
- d) *Proportion of participants intending to reduce alcohol consumption*: we hypothesise that there will be a greater change in the *proportion* of intervention participants, relative to control, intending to reduce their next-month alcohol consumption between baseline and immediately post-intervention (15).
- e) *Proportion of participants intending to reduce alcohol consumption*: we hypothesise that there will be a greater change in the *proportion* of intervention participants, relative to control, intending to reduce their next-month alcohol consumption between baseline and 4-weeks (15).
- f) *Change in knowledge of alcohol as a breast cancer risk factor (alcohol-breast cancer literacy)*: we hypothesise that there will be a greater change in the proportion of intervention participants accurately identifying alcohol as a risk factor for breast cancer between baseline and 4-weeks, compared to control participants.

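### Does the overall group-by-time Wald test leave open which result decides the primary outcome?

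*SAP*

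**What the plan says.** The SAP, under Analytic approach, fits a mixed model with treatment, time and their interaction. It says that inference "will be based on a comparison, between treatment groups, of change in outcomes from baseline to immediate post-intervention", and then adds week 4 with an and/or. After the text on covariance structures and the fallback to estimating equations comes one sentence on testing: "A Wald test (or equivalent approach) will be used to test for an overall group by time interaction in outcomes".

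The outcome lists separate the two time points. The primary outcome is "Change in next-month drinking intentions (immediate post-intervention"); secondary outcome 1 is "Change in next-month drinking intentions (4-weeks post-randomisation"). Secondary outcomes 3 and 4 split the proportion intending to reduce in the same way, starting with "Proportion of participants intending to reduce their next-month alcohol consumption (immediate post-intervention").

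In the protocol, section 3.1 states the primary hypothesis as a greater change in the intervention arm, "relative to control, between baseline and immediately post-intervention (likert scale response item"). The power statement in section 4.2 concerns the same interval: a change of 1.00 against 0.26. The immediate assessment is short, "comprising only the set of intention questions containing the primary outcome item". The schedule in section 6.2 shows the Likert item at all three times, and the statistical analyses paragraph in section 4.2 mentions all three.

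**The concern.** A SAP should leave no doubt about which statistic decides the primary outcome. This one names a single test, and that test is not tied to a time point. The item is measured three times, and analysis waits until the 4-week assessments are in, so one three-time model is a natural reading. Its interaction then has (2 − 1) × (3 − 1) = 2 degrees of freedom, one of which belongs to secondary outcome 1.

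Two p-values would then be available for the primary item. The overall one could be significant because of week 4 alone. It could also miss an immediate effect of the planned size that partly fades. If the choice were made after seeing the data, the trial's headline could depend on it. Secondary outcomes 3 and 4 are in the same position. Outcomes measured only at baseline and week 4 are not, because their interaction has 1 degree of freedom.

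**Working it through.** **Inputs from protocol section 4.2.** Difference in change 1.00 − 0.26 = 0.74; SDs 1.18 (pre) and 1.22 (post); two-sided alpha 0.05; 5% attrition and 30% non-drinkers. Evaluable per arm: 39 × 0.95 × 0.70 = 25.9, taken as 26; 45 × 0.95 × 0.70 = 29.9, taken as 30.

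**Assumptions, not in the documents.** Correlation ρ between measurements; week-4 SD of 1.22; no extra dropout at week 4.

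**Step 1: the plan's own power.** Variance of change = 1.18² + 1.22² − 2ρ × 1.18 × 1.22. At ρ = 0.7 this is 2.8808 − 2.0154 = 0.8654, so the SD is 0.930. The noncentrality is 0.74 / (0.930 × √(2/26)) = 2.87 on 50 df, giving 80.3% power. With 30 per arm it is 3.08 on 58 df, giving 85.8%. These agree with the stated 80% and 85%. Other correlations do not: with 26 per arm, power is 58.7% at ρ = 0.5, 68.3% at 0.6 and 93.1% at 0.8. So ρ of about 0.7 is back-solved, and the 80% is an input to what follows. The stated sample size fits a 1-df comparison of the immediate change.

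**Step 2: the overall test with two times.** It has 1 df and is the primary contrast. Nothing differs.

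**Step 3: the overall test with three times.** Take ρ = 0.7 for every pair of times. The covariance of the immediate and week-4 changes is 0.7 × 1.22² − 2 × 0.7 × 1.18 × 1.22 + 1.18² = 0.419, so their correlation is r = 0.419 / 0.865 = 0.484. For true differences d₁ (immediate) and d₂ (week 4), the noncentrality is

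λ = (n/2)(d₁² − 2r·d₁d₂ + d₂²) / [s²(1 − r²)],

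referred to F(2, 2n − 3). For d₁ = 0.74 and d₂ = 0.37: 13 × 0.4195 / 0.6626 = 8.23.

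| d₁ | d₂ | λ | Overall test significant | Immediate contrast significant |
|---|---|---|---|---|
| 0.74 | 0 | 10.74 | 81.9% | 80.3% |
| 0.74 | 0.185 | 8.82 | 73.4% | 80.3% |
| 0.74 | 0.37 | 8.23 | 70.2% | 80.3% |
| 0.74 | 0.555 | 8.99 | 74.3% | 80.3% |
| 0.74 | 0.74 | 11.09 | 83.2% | 80.3% |
| 0 | 0.185 | 0.67 | 10.1% | 5% |
| 0 | 0.37 | 2.69 | 27.6% | 5% |

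In a simulation with 26 per arm (400,000 draws, chi-square version, common SD 1.2, ρ = 0.7) and half the effect kept at week 4, the immediate contrast was significant and the overall test was not in about 10% of trials.

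**Step 4: how far the range could stretch.** Setting r to 0.7 gives up to 94% power, and 39% significant with no immediate effect and d₂ = 0.37. With equal SDs of change, that needs an immediate-to-week-4 correlation of (0.7 × 0.865 + 2.015 − 1.392) / 1.488 = 0.83. Answers four weeks apart would then agree more closely than answers minutes apart (0.7). The documents give no reason to expect that.

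**Step 5: does the plan lead to the overall p-value?** The loss needs two decisions: one three-time model, and its overall p-value reported as the primary result. The schedule makes the model plausible. The reporting rule appears nowhere and conflicts with the outcome lists: a single pooled p-value cannot be the result both for the immediate change (primary) and for the week-4 change (secondary outcome 1). Read alongside the inference sentence, the hypothesis and the power statement, the overall test is a general screen that sits beside the time-specific contrasts.

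**The case for a change.** The best case for a change is that the documents point to the immediate contrast without ever naming it as the deciding test. The inference sentence allows immediate and/or week 4, and the one named statistic is a different quantity in a three-time model. With about 26 evaluable women per arm the two tests will sometimes disagree, and one sentence would settle the matter at no cost in data or sample size.

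Part of this stands. The Wald sentence is the only named test, neither document states how many times enter the primary model, and a linking sentence would do no harm. The and/or is weaker evidence. The SAP is covering outcomes with different schedules, and its design section limits the immediate assessment to drinking intentions. For that item both times apply, but each is listed as its own outcome.

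The case where week 4 alone drives significance is not an inflated error rate of the overall test, because its null hypothesis is false there. It assumes no immediate effect and a later one, the reverse of what the protocol plans for. A near-zero immediate estimate would also be visible, since that change is itself the listed primary outcome. The protocol's introduction reports the earlier trial's primary outcome, "with a significantly greater increase in the intervention arm", with an arm-by-time p-value. That result was for change from baseline to 4 weeks, so it says nothing about how this three-time item will be tested.

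**Conclusion.** No change is needed. The SAP omits a sentence linking the overall interaction test to the primary outcome, but its outcome lists and inference statement, with the protocol's hypothesis and power calculation, identify one contrast: the between-group difference in change from baseline to immediately post-intervention. The planned model supplies it, and the stated sample size matches it at an assumed correlation of about 0.7. Analysts who follow the documents will report that contrast as primary and week 4 separately, and the same reading serves secondary outcomes 3 and 4.

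If the overall p-value were used instead in a three-time model, power for the planned effect would move from 80% to between about 70% and 83%. With no immediate effect, a week-4 difference of 0.185 or 0.37 would give significance in about 10% or 28% of trials. Those figures rest on a correlation of 0.7 throughout, a week-4 SD of 1.22, no extra dropout, and a reporting decision that the plan does not make.
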